## Statistical Design and Powers

Our *a priori* power analysis is based on two previous studies in our lab that delivered similar foreign language or music intervention during the same period in development with behavioral/electrophysiological outcome measures post intervention [7,24]. In both studies, the comparisons were only at post-intervention between the intervention group and the control group. In the language intervention study, the intervention group exhibited higher consonant discrimination ( $M=65.7$ ,  $SE=2.4$ ) than control ( $M=56.7$ ,  $SE=2.3$ ) and in the music intervention, the main effect of intervention in the ANOVA model had an effect size  $\eta^2$  of 0.12. Using the G\*Power software, it shows that to detect a similar between group effect, a total of 40 subjects at a level significance level of 0.05 will yield power above 0.90.

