## Study Protocol

The objective of the proposed music intervention is to standardize the procedures in which the intervention is carried out such that 1) it matches the music intervention in our previous study and that 2) it can be replicated in the future to include new outcome measures.

The data from this intervention will be compared to a control group and we hypothesize that the intervention group will exhibit enhanced post-intervention measurement at 11 months of age in comparison to the control group.

Families with healthy infants with no family history of hearing, speech and communication disorders will be recruited at 7 months of age to participate in the longitudinal music intervention study (Aim 2) that will last for about 4 months. At recruitment, infants with 3 or more ear infections and infants who have already been/ have had participated in infant music classes will be excluded.

Infants will complete a pre-intervention brainstem measures at 7 months of age upon enrolling in the study: the frequency-following response measure (FFR). Participants will have to complete the measurement to proceed to the intervention phase.

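### Power above 0.90 with 40 infants does not follow from the cited music-study effect (about 0.62 two-sided, 0.74 one-sided) and cannot be reproduced from the plan

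*Combined protocol and SAP*

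**What the plan says.** Statistical Design and Powers bases the calculation on two earlier studies from the same lab and notes that in both "the comparisons were only at post-intervention between the intervention group and the control group". For the language study it says that "the intervention group exhibited higher consonant discrimination", with means of 65.7 (SE 2.4) and 56.7 (SE 2.3) and no group sizes. For the music study it says that "the main effect of intervention in the ANOVA model had an effect size" (eta-squared) of 0.12. It then reports from G*Power that, for a similar between-group effect, "a total of 40 subjects at a level significance level of 0.05 will yield power above 0.90".

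Study Protocol says the intervention is to be standardised so that "it matches the music intervention in our previous study". Its hypothesis is that "the intervention group will exhibit enhanced post-intervention measurement at 11 months of age in comparison to the control group".

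The plan does not state which of the two effects was entered, the G*Power test chosen, one- or two-sided testing, the allocation ratio, whether 0.12 is a partial or classical eta-squared, any correlation between repeated measures, or an allowance for dropout.

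**The concern.** The power sentence is the plan's only sample-size justification. The trial is built to match the earlier music intervention, so the music effect is the more relevant of the two cited inputs. An eta-squared of 0.12 in a two-group comparison is a standardised difference of about 0.74, and 20 per group is too few to detect that with 90% power.

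If the true effect equals the earlier music effect, an unadjusted 20 vs 20 comparison misses it about 38% of the time two-sided (1 − 0.62) or 26% one-sided (1 − 0.74). The plan implies under 10%. A reader who relies on the stated power could take a null result as stronger evidence against the intervention than it is.

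**Working it through.** **Inputs from the plan (Statistical Design and Powers):** total N = 40; alpha = 0.05; stated power above 0.90; music study eta-squared 0.12; language study means 65.7 and 56.7, SEs 2.4 and 2.3.

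**Assumptions where the plan is silent:** 20 vs 20; all 40 infants analysed; one unadjusted comparison at 11 months, the time point named in the hypothesis; 0.12 read as partial. Both one- and two-sided tests are shown, because the hypothesis is directional.

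**1. Stated figure from the music effect**

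- f = √(0.12/0.88) = 0.369; d = 2f = 0.739.
- Noncentrality = d × √(20×20/40) = 0.739 × 3.162 = 2.335, with 38 df.
- Power from the noncentral t: **0.624 two-sided, 0.742 one-sided**. The stated value above 0.90 is not reproduced.
- Equal allocation is the most favourable split: 15 vs 25 gives 0.596 two-sided and 0.718 one-sided.

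**2. What 0.90 would require at this effect**

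- Two-sided: N = 78 gives 0.896, N = 80 gives 0.904. One-sided: N = 64 gives 0.899, N = 66 gives 0.907.
- With 20 vs 20, 0.90 is reached at d = 1.05 two-sided (eta-squared 0.217) or d = 0.94 one-sided (eta-squared 0.182).

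**3. The language effect**

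With n per group in that study, assumed equal, SD = √(n × (2.4² + 2.3²)/2) and d = 9.0/SD. Power in the present trial at 20 vs 20:

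| Assumed n per group | d | Two-sided | One-sided |
|---|---|---|---|
| 13 | 1.062 | 0.905 | 0.951 |
| 14 | 1.023 | 0.884 | 0.937 |
| 16 | 0.957 | 0.839 | 0.908 |
| 17 | 0.929 | 0.816 | 0.892 |
| 20 | 0.856 | 0.751 | 0.845 |
| 25 | 0.766 | 0.655 | 0.768 |

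This effect supports the claim only with 13 or fewer per group two-sided, or 16 or fewer one-sided.

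**4. Other routes to 0.90 with N = 40 and eta-squared 0.12**

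- *Adjusting for the 7-month FFR*, correlation r: noncentrality λ = 40f²/(1 − r²), 37 df. Two-sided, r = 0.71 gives 0.898 and 0.72 gives 0.906. One-sided, r = 0.62 gives 0.899 and 0.63 gives 0.904. At r = 0.5 power is 0.75 and 0.84.
- *Classical eta-squared*, with share q of the variance in other model terms: partial value = 0.12/(1 − q). Power reaches 0.902 two-sided at q = 0.45 and 0.900 one-sided at q = 0.34.
- *Repeated-measures between-group test on the 7- and 11-month values*, correlation ρ: λ = 40f² × 2/(1 + ρ). At ρ = 0 power is 0.896 two-sided and 0.945 one-sided; at ρ = 0.2, 0.836 and 0.906; at ρ = 0.5, 0.748 and 0.842. This treats the effect as equally present before the intervention. If it exists at 11 months only, the effective d is (d/2)/√((1 + ρ)/2), and one-sided power is 0.49 at ρ = 0 and 0.43 at ρ = 0.2.
- *Group-by-time interaction*, entering f = 0.369 with ρ = 0.5: 0.995. This is a different test from the between-group effect that the plan names.
- *Several measures per infant at 11 months*, k measures: λ = 40f² × k/(1 + (k − 1)ρ). Two-sided power is 0.915 for three measures at ρ = 0.2 and 0.931 for four at ρ = 0.25, but 0.796 and 0.821 at ρ = 0.5.
- *40 per group instead of 40 in total*: 0.904 two-sided. A mix-up of the two is possible, but nothing in the plan shows it.

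**The case against.** The strongest reply is that this is under-reporting, not a wrong number. The plan cites two effects and does not say which was used. If the language study was small enough, its effect justifies the sentence by itself. The phrase about a main effect in an ANOVA model suggests other terms were present, so 0.12 may be a classical eta-squared; 0.62 would then be the value when those terms explain nothing. This trial also measures FFR at both 7 and 11 months, so an adjusted analysis is plausible, and several response measures per infant could be analysed together.

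Much of this stands. The figure is not shown to be impossible, no slip in calculation has been demonstrated, and the routes listed here may not be exhaustive. But each route needs an input that the plan does not give: a group size, a correlation, a variance share or a number of measures. If the language effect was the one entered, the plan should say so, because its wording implies that 40 infants suffice for an effect like that in either study. The earlier comparisons were made only after the intervention, and the present hypothesis names the 11-month comparison. The unadjusted between-group test is therefore the plan's own framing.

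**Conclusion.** The concern holds. With 40 infants split equally, no covariate, partial eta-squared 0.12 and every infant analysed, power is 0.62 two-sided or 0.74 one-sided, which is 28 or 16 percentage points short of 0.90. The language effect cannot settle the matter without that study's group sizes. The stated power is unsupported by the more relevant of its two cited inputs and cannot be reproduced from the plan. Because it is the only sample-size justification, it must be corrected or documented. Losses would lower these values further: infants must complete every session to be measured afterwards, and no dropout allowance is given.

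**What to change.** Restate the power sentence with the G*Power test, sidedness, allocation, the effect size entered and its source, whether 0.12 is partial or classical, and the power at eta-squared 0.12.

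- If the authors confirm a two-sided, 1:1, unadjusted test and a partial eta-squared, suitable wording is: *With 40 analysable infants (20 per group) and two-sided alpha 0.05, power is about 0.62 for eta-squared 0.12 (d = 0.74); 0.90 power is available for d of about 1.05 or more.*
- If they confirm a one-sided test, the figures become 0.74 and d of about 0.94.
- If the language-study effect was used, add that study's group sizes.
- If a baseline-adjusted or repeated-measures model was used, add the assumed correlation and the number of measures.

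The cost is one or two sentences and a less favourable stated power. No extra infants are needed for this correction.
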